1. BACKGROUND

Hemophilia A is an X-linked recessive bleeding disorder that occurs in approximately 1 in 5,000 live male births. Patients with hemophilia A have a deficiency or absence of blood coagulation factor VIII (FVIII), an essential component of the intrinsic pathway in the coagulation cascade ([Franchini and Mannucci 2013](#)).

The development of inhibitory alloantibodies (inhibitors) occurs in approximately 20%–30% of patients with severe hemophilia A and in 3%–13% of those with moderate or mild disease ([Franchini and Mannucci 2013](#)). Inhibitors neutralize the activity of endogenous FVIII as well as of FVIII administered as replacement therapy. For patients with a history of high-titer (≥ 5 BU/mL) inhibitor following a re-challenge with FVIII administration (high-responding inhibitor), the only hemostatic options currently available are pro-thrombotic coagulation factors that augment other parts of the coagulation cascade (i.e., “bypassing agents”).

Current standard prophylactic regimens commonly use infusion therapy administered three times a week; other regimens require daily or every other day administration, depending on the patient’s needs ([Shapiro 2013](#)). Major issues with current regimens are the need for adequate venous access and patient/family compliance with regular prophylaxis, especially in the very young pediatric population, in whom central venous access devices (CVADs) have been used to overcome technical difficulties. Thus, both the disease and its treatment have the potential to affect health-related quality of life (HRQoL), the latter through limitations on daily activities that treatment may impose.

The development of effective prophylactic treatment options with decreased immunogenicity and less frequent dosing requirements is a high unmet medical need in the population of hemophilia A patients with FVIII inhibitors. Given the significant unmet medical need among pediatric patients with hemophilia A with FVIII inhibitors and positive benefit-risk assessment for emicizumab, initiation of a pediatric Phase III study is appropriate.

Emicizumab is a recombinant, humanized, bispecific, immunoglobulin G4 (IgG4) monoclonal antibody that binds with moderate affinity to activated factor IX (FIXa) and factor X (FX), mimicking the co-factor function of FVIII. In patients with hemophilia A, hemostasis can be restored irrespective of the presence of FVIII inhibitors, as emicizumab shares no sequence homology with FVIII. In addition, emicizumab offers the possibility of subcutaneous (SC) administration, removing the need for venous access. Finally, because of the expected pharmacokinetic properties of this antibody, markedly extending the dosing interval to once weekly or even less frequently, this novel compound has the potential to dramatically change the treatment of patients with hemophilia A with and without FVIII inhibitors who are in need of effective, safe, and convenient prophylactic therapy.

Currently available experience with emicizumab in humans includes data from one Phase I study (Study ACE001JP), its ongoing extension, a Phase I/II study (Study ACE002JP), and a site of injection and relative and absolute bioavailability study in healthy Japanese subjects (Study JP29574). See Protocol Section 1.2 for detailed description of the study results ([Shima et al. 2016](#)). On the basis of these compelling Phase I/II data, a clinical development program in adult and pediatric patients with hemophilia A (both with and without FVIII inhibitors) has been initiated. Four Phase III studies are currently ongoing and are aimed at evaluating the efficacy and safety of emicizumab at various dosing regimens and in different populations. The studies are Study BH29884, which evaluates 1.5 mg/kg weekly (QW) in an adult and adolescent population with FVIII inhibitors; Study BH29992, which evaluates 1.5 mg/kg QW, 3mg/kg every 2 weeks (Q2W) and 6mg/kg every 4 weeks (Q4W) in pediatric patients with inhibitors; Study BH30071, which evaluates 1.5mg/kg QW and 3mg/kg Q2W in a population without inhibitors; and Study BO39182, which evaluates 6mg/kg Q4W in a population with or without inhibitors.

[REDACTED] meetings have been held with United States Food and Drug Administration (FDA) to discuss the development program of emicizumab. [REDACTED]

[REDACTED] The Paediatric Investigational Plan (PIP) was submitted to EMA/Paediatric Committee (PDCO) on 10 August 2015. On [REDACTED], the protocol for this study (plus the Informed Consent Form [ICF] and assent forms) was sent to the FDA, and the core Clinical Trial Application (CTA) was dispatched to the affiliates on [REDACTED].

On 16 November, 2017, the FDA approved the Biologics License Application (BLA) for HEMLIBRA (emicizumab-kxwh) for routine prophylaxis to prevent or reduce the frequency of bleeding episodes in people with haemophilia A with factor VIII inhibitors (PwHAI). In addition, on 27 February, 2018, the European commission approved Hemlibra® (emicizumab) for routine prophylaxis of bleeding episodes in people with haemophilia A with factor VIII inhibitors.

2. STUDY DESIGN

This non-randomized, multicenter, open-label, Phase III clinical study will enroll children with hemophilia A who have inhibitors against FVIII. Children with hemophilia A and documented historical FVIII inhibitor titer (≥ 5 BU) must currently be receiving treatment with bypassing agents. At least 40 patients younger than 12 years of age and up to approximately 80 patients are planned for enrolment, with allowance for patients 12-17 years of age who weigh < 40 kg at the time of informed consent. Patients will receive weekly SC doses of emicizumab at 1.5 mg/kg QW (Cohort A) for a minimum of 52 weeks or until unacceptable toxicity, discontinuation from the study due to any cause, or other criteria set forth in the protocol, whichever occurs first (see [Figure 1](#)). After 52

weeks of treatment, an individual patient who continues to derive clinical benefit may continue receiving prophylactic emicizumab as part of this study or a future separate emicizumab extension study.

Because of the uncertainty of the dosing regimen needed in patients < 12 years of age or < 40 kg to achieve similar exposure as in adults and adolescents, this study will first evaluate the appropriate dosing regimen in children by starting with the same weekly dosing regimen (1.5mg/kg QW) being evaluated in the Phase III study (Study BH29884) in adult and adolescent patients with hemophilia A with inhibitors. Emicizumab will be administered with a weekly loading dose of 3.0 mg/kg QW for the first 4 weeks (Day 1 of each week) followed by a maintenance dose of 1.5 mg/kg QW (Cohort A) for the remainder of the treatment period (Day 1 of each week). Individual patients may have their dose up-titrated if they experience suboptimal bleeding control on emicizumab. Investigators will monitor patients regularly with the guidance of an up-titration algorithm. If patients meet protocol-defined criteria for efficacy-guided up-titration, the investigator will contact the Medical Monitor to initiate a discussion about possible up-titration.

In a first interim data review, the appropriateness of the initial dosing regimen will be evaluated (maintenance dose of 1.5 mg/kg QW) after the first 3-5 patients (≥ 2 to < 12 years of age) have been dosed for a minimum of 12 weeks. A Joint Monitoring Committee (JMC) will review all cumulative data (e.g., safety, efficacy, and pharmacokinetics) at the first interim data review and provide recommendations on increasing the starting maintenance dose if a majority of the first 3-5 patients fail to achieve optimal control of bleeds after the first 12 weeks of treatment or their plasma emicizumab trough concentration is lower than the one being targeted in adolescents and adults (i.e., 45 μ g/mL). All patients enrolled following the first interim data review will receive the starting maintenance dose selected/confirmed by the JMC. Patients enrolled prior to the first interim data review will remain on their current maintenance dose unless they meet eligibility for up-titration based on protocol-defined criteria.

In order to include and safely treat the youngest patients (birth to < 2 years of age), this study will include a staggered approach to enrolment by age. Patients ≥ 2 to < 12 years of age and patients 12-17 years of age who weigh < 40 kg will enroll first. A second interim data review will occur once at least 10 patients between ≥ 2 and < 12 years of age have been dosed for a minimum of 12 weeks, at which time all cumulative data (e.g., safety, efficacy, and pharmacokinetics) will be evaluated by the JMC to provide recommendations for enrolment of children < 2 years of age, as well as recommendations on any additional adaptations of the maintenance dose, if necessary.

[figure not shown]
If patient recruitment is faster than anticipated, enrolment will be placed on a temporary hold following the first 20 patients until the JMC releases its recommendations on the appropriateness of the maintenance dose (Cohort A). After the JMC recommendations

are released following both interim data reviews, the study will continue to enrol in Cohort A up to a maximum of approximately 60 patients.

Once 1) the exposure at 1.5 mg/kg QW has been characterized in this pediatric population; 2) Cohort A is fully enrolled; and 3) review of data in adults and adolescents from two ongoing Phase III studies evaluating emicizumab at 3 mg/kg Q2W (BH30071) and 6 mg/kg Q4W (BO39182) identifies no safety concerns, this study will open two additional non-randomized cohorts to investigate Q2W and Q4W regimens in pediatric patients. Parallel enrolment with alternate cohort allocation to Cohort B (3 mg/kg Q2W) and Cohort C (6 mg/kg Q4W) will occur, for a total of approximately 10 patients per cohort. Of note, enrolment to Cohorts B and C will be limited to patients 2-11 years of age. Emicizumab will be administered with a loading dose of 3 mg/kg QW for the first 4 weeks followed by a maintenance dose of 3 mg/kg Q2W (Cohort B) and 6mg/kg Q4W (Cohort C) for a minimum of 52 weeks, or until unacceptable toxicity, discontinuation from the study due to any cause, or other criteria set forth in the protocol, whichever occurs first (see [Figure 1](#)). Individual patients may have their dose up-titrated if they experience suboptimal bleeding control on emicizumab. The entire study will enrol up to approximately 80 patients .

All patients will continue to receive prior therapy as prescribed by their treating physician with episodic bypassing agents to treat breakthrough bleeds as needed. However, prophylactic use of bypassing agents should be discontinued by the time the first dose of emicizumab is given.

Figure 1 Study Schema

JMC = Joint Monitoring Committee; Q2W = every 2 weeks; Q4W = every 4 weeks; QW = once weekly; Scr = screening.

* In a first interim data review, the starting maintenance dose will be re-evaluated after the first 3–5 patients (≥ 2 to < 12 years of age) have been dosed for a minimum of 12 weeks. A JMC will review all cumulative data (e.g., safety, efficacy, and pharmacokinetics) to provide recommendations on increasing the starting maintenance dose. A second interim data review by the JMC will occur once at least 10 patients (≥ 2 to < 12 years of age) have been dosed for a minimum of 12 weeks, at which time all available cumulative data (e.g., safety, efficacy, and pharmacokinetics) will be evaluated to provide recommendations for the enrolment of children < 2 years of age, as well as on the maintenance dose. If patient recruitment is faster than anticipated, enrolment will be placed on a temporary hold after the first 20 patients until the JMC releases its recommendations on the appropriateness of the maintenance dose. After the JMC recommendations are released following both interim data reviews, the study will continue to enroll up to a maximum of approximately 60 patients in Cohort A. Subsequently, should no safety concerns arise from review of adult/adolescent data at Q2W (BH30071) and Q4W (BO39182) dosing, parallel enrolment with alternate cohort allocation to Cohorts B and C (up to approximately 10 patients per cohort) will commence.

The primary analysis for all cohorts will be performed 52 weeks after all patients in the primary population of Cohort A have been enrolled or withdrawn prematurely, whichever occurs first (see Section [2.5](#)). The primary population of Cohort A consists of all patients enrolled prior to the close of enrolment for patients ≥ 2 years of age (up to approximately 60 patients) and is used to define the timing of the primary analysis of the study. The efficacy analysis will evaluate the clinical effect of prophylactic emicizumab on the number of bleeds over time (i.e., bleed rate) and will characterize the efficacy of up-titration on an intra-patient and population level. If no patients < 2 years of age are included in the primary population of Cohort A, the primary analysis will still occur at the specified time; however, enrolment to Cohort A may be left open exclusively for patients < 2 years of age in order to enrol approximately 5 such patients. Note that these patients will be included in the primary analysis of Cohort A regardless of their follow-up time. Additionally, all available data from patients enrolled in Cohorts B and C (regardless of their follow-up time) will be included at the time of the primary analysis.

In order to complement the analysis of Study BH29884 in adult and adolescents with inhibitors an interim analysis will be performed for Study BH29992 at the same time as the primary analysis of Study BH29884. An interim clinical study report (CSR) will be written for Study BH29992, in which some analyses may differ from the final study analyses. These differences are outlined in this SAP.

Other interim analyses might occur at any time in order to support health authorities' requests or submissions.

2.1 PROTOCOL SYNOPSIS

The Protocol Synopsis is in [Appendix 1](#).

2.2 COLLECTION OF BLEED AND MEDICATION DATA

Bleed and medication data are collected through a bleed and medication questionnaire (BMQ), which was developed by the Sponsor given that no standard questionnaire for collection of these data was available.

The BMQ was developed as a patient-reported outcome measure of bleeding episodes (including cause, type, and location of bleeds) and hemophilia-related medication use. The draft questions were developed following a review of the hemophilia A literature and discussions with medical professionals regarding what information related to bleeds was most important to capture.

The BMQ is completed by the caregiver, with use of an electronic handheld device. All bleeds, hemophilia related medications, and emicizumab administrations are entered at minimum weekly and as they occur. If a patient does not experience a bleed or does not receive any hemophilia related medications for a week, the caregiver will be prompted to log in to the device and confirm this. Of note, the caregiver is able to enter bleeds and medications for the past 8 days, including the day entries are made. This retrospective data entry window was considered acceptable in terms of recall bias and was added in order to optimize the completeness of data collection.

The caregiver is able to edit and delete bleeds and medications immediately after they are entered. However, if the data have been submitted to the vendor's database (i.e., after responses have been confirmed by the caregiver), the caregiver is no longer able to edit or delete the data. Furthermore, the investigator, the caregiver, and the patient are instructed to review the data together at every clinic visit. If the caregiver was unable to enter bleed, medication, or emicizumab data within the 8 days' timeframe, if the caregiver mistakenly entered data that require deletion, or if the caregiver mistakenly entered data that require modification (e.g., incorrect emicizumab dose), the investigator is able to submit a data clarification request (DCR) to the vendor on the caregiver's behalf at any time.

Furthermore, the Sponsor's data manager and Medical Monitor will review the data entered by the caregiver on the BMQ for inconsistencies against data collected on the electronic case report form (eCRF) or to identify obvious data points to be clarified (e.g., missing entry of the weekly emicizumab injection). These clarification requests are sent to the investigator, who reviews them together with the caregiver and the patient (if the patient is old enough) and may enter or change the data via a DCR, if necessary. In addition, HRQoL using the Haemo-QoL-Short Form (SF) (completed by patients aged 8 years and above), proxy-reported HRQoL and the Adapted InhibQoL including Aspects of Caregiver Burden questionnaire (completed by caregivers for all children), and the number of days of missed daycare/school (completed by caregivers for all children) will be assessed every 3 months as outlined in the schedule of assessments. The number

of days the child was hospitalized (if applicable) will be derived from data collected on eCRF.

The Haemo-QoL-SF, Adapted InhibQoL including Aspects of Caregiver Burden questionnaires, and number of days of missed daycare/school are completed with use of a tablet at the site during clinic visit. However, for this type of data, there is no possibility for retrospective data entry or data modification and these data will not be queried.

2.3 OBJECTIVES AND ENDPOINTS

2.3.1 Efficacy Period for All the Endpoints

The start of the efficacy period for each individual patient is defined as the day of the first emicizumab dose.

The end of the efficacy period is defined as the date of the clinical cutoff or the date of withdrawal from the initial study period (i.e., treatment period according to eCRF), whichever is earlier. For patients who withdraw from the study before reaching the Week 1 visit, the duration of efficacy period is set to 1 day and it starts and ends on the day of enrolment.

For patients whose dose is up-titrated, the bleeds on the up-titrated dose are analyzed separately. The efficacy period on a given up-titrated dose starts with the first day on this dose and ends on the day of the clinical cut-off, the date of withdrawal, or on the last day on this specific dose, whichever is earlier.

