Once 1) the exposure at 1.5 mg/kg QW has been characterized in this pediatric population; 2) Cohort A is fully enrolled; and 3) review of data in adults and adolescents from two ongoing Phase III studies evaluating emicizumab at 3 mg/kg Q2W (BH30071) and 6 mg/kg Q4W (BO39182) identifies no safety concerns, this study will open two additional non-randomized cohorts to investigate Q2W and Q4W regimens in pediatric patients. Recruitment to Cohort B (3 mg/kg Q2W) and Cohort C (6 mg/kg Q4W) will occur in parallel with alternate cohort allocation via IxRS, for a total of approximately 10 patients per cohort. Of note, enrollment to Cohorts B and C will be limited to patients 2–11 years of age. Emicizumab will be administered with a loading dose of 3 mg/kg QW for the first 4 weeks followed by a maintenance dose of 3 mg/kg Q2W (Cohort B) and 6 mg/kg Q4W (Cohort C) for a minimum of 52 weeks, or until

unacceptable toxicity, discontinuation from the study due to any cause, or other criteria set forth in the protocol, whichever occurs first (see *Figure 1*). During the 52-week treatment period, individual patients may have their dose up-titrated if they experience suboptimal bleeding control on emicizumab.

The entire study will enroll up to approximately 80 patients with allowance for additional patients < 2 years of age in Cohort A.

A patient who fulfills the inclusion and exclusion criteria should be enrolled at the Week 1 visit. Prophylactic use of bypassing agents should be discontinued *the day before* the first dose of emicizumab is given.

Figure 1 Study Schema

JMC=Joint Monitoring Committee; Q2W=*every 2 weeks*; Q4W=*every 4 weeks*; QW=*once weekly*; Scr=*screening*.

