* In a first interim data review, the starting maintenance dose will be evaluated after the first 3–5 patients (≥ 2 to < 12 years of age) have been dosed for a minimum of 12 weeks. A JMC will review all cumulative data (e.g., safety, efficacy, and pharmacokinetics) to provide recommendations on increasing the starting maintenance dose. A second interim data review will occur by the JMC once at least 10 patients (≥ 2 to < 12 years of age) have been dosed for a minimum of 12 weeks, at which time all available cumulative data (e.g., safety, efficacy, and pharmacokinetics) will be evaluated to provide recommendations for the enrollment of children < 2 years of age, as well as on the maintenance dose. Should patient recruitment be faster than anticipated, enrollment will be placed on a temporary hold after the first 20 patients until the JMC releases its recommendations on the appropriateness of the maintenance dose. After the JMC recommendations are released following both interim data reviews, the study will continue to enroll up to a maximum of approximately 60 patients in Cohort A. Subsequently, should no safety concerns arise from review of adult/adolescent data at Q2W (BH20071) and Q4W (BO39182) dosing, parallel enrollment with alternate cohort allocation to Cohorts B and C (up to approximately 10 patients per cohort, respectively) will commence.

The primary analysis for all cohorts will be performed 52 weeks after all patients in the primary population of Cohort A have been enrolled or withdrawn prematurely, whichever occurs first. The primary population of Cohort A consists of all patients enrolled prior to the close of enrollment for patients ≥ 2 years of age (up to approximately 60 patients) and is used to define the timing of the primary analysis of Cohorts A, B, and C. If no patients < 2 years of age are included in the primary population of Cohort A, the primary analysis will still occur at the specified time; however, enrollment to Cohort A may be left open exclusively for patients < 2 years of age in order to enroll approximately 5 such patients. Note that these patients will be included in the primary analysis of Cohort A regardless of their follow-up time. Additionally, all available data from patients enrolled in Cohorts B and C (efficacy period approximately 6 months) will be included in the primary analysis of Cohort A.

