3.2 END OF STUDY AND LENGTH OF STUDY

LENGTH OF STUDY

The length of the entire study from screening of the first patient to the last patient completing 52 weeks in the study and/or the end of study follow-up visit (24 weeks after discontinuing emicizumab) will be approximately 152 weeks.

END OF STUDY

The primary analysis will take place at the same time for Cohorts A, B, and C. It will occur after all patients in the primary population of Cohort A have completed 52 weeks of treatment, or have withdrawn prematurely, whichever occurs first. All data from patients enrolled in Cohorts B and C will be included regardless of follow-up time.

After 52 weeks of treatment, an individual patient who continues to derive clinical benefit may continue receiving prophylactic emicizumab as part of this study or a future

separate emicizumab extension study. Patients who discontinue emicizumab will have a safety follow-up visit at 24 weeks after the last emicizumab dose.

The end of this study is defined as the date when the last remaining patient has completed the last visit (i.e., LPLV), as defined below:

- Completed 52 weeks of emicizumab and either transferred to a separate extension study to receive further emicizumab as per Roche Global Policy on Continued Access to Investigational Medicinal Products or to commercial product

OR

- Completed the end of study safety follow-up visit 24 weeks after discontinuing emicizumab

OR

- Consent has been withdrawn

OR

- Lost to follow-up

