ACE910=emicizumab.

- Joint bleed
- Non-joint bleed

The exposure-response relationship of emicizumab was quantitatively characterized and simulations suggested that a median ABR of 0 is achieved for emicizumab trough plasma concentration $\geq 45 \mu\text{g/mL}$. On the basis of population PK modeling, a median trough plasma concentration of $45 \mu\text{g/mL}$ is predicted to be achieved after treatment with 4 weekly doses of 3 mg/kg and maintained, thereafter, with weekly doses of 1.5 mg/kg.

The loading doses of 3 mg/kg weekly for 4 weeks were chosen in order to rapidly achieve the effective trough concentration of 45 µg/mL without exceeding the maximum dose of 3 mg/kg weekly investigated in the Phase I/II studies. Thereafter, a dose and schedule of 1.5 mg/kg weekly was chosen in order to reduce the peak-trough fluctuations and to maintain emicizumab plasma concentrations above 45 µg/mL over the entire dosing interval. This dosing regimen (i.e., 3 mg/kg weekly for 4 weeks followed by 1.5 mg/kg weekly) was, therefore, chosen to be investigated in the adult and adolescent study, BH29884.

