4.5.2 Dosage, Administration, and Compliance

Emicizumab treatment will begin with a loading dose of 3 mg/kg QW for the first 4 weeks (Day 1 of each week) followed on Week 5 by a maintenance dose of either 1.5 mg/kg QW (Cohort A), 3 mg/kg Q2W (Cohort B), or 6 mg/kg Q4W (Cohort C). Note that the cumulative dose studied in all three cohorts is identical, but the dose administration schedule differs between cohorts. Patients will receive prophylactic emicizumab for a minimum of 52 weeks, or until unacceptable toxicity or discontinuation from the study due to any cause.

On 7 December 2016, the JMC recommended continued enrollment to Cohort A at the original starting maintenance dose of 1.5 mg/kg QW, and to open enrollment to patients < 2 years of age at that same maintenance dose. Moreover, review of data in adults and adolescents from two ongoing Phase III studies evaluating emicizumab at 3 mg/kg Q2W (BH30071) and 6 mg/kg Q4W (BO39182) has identified no safety concerns to date. See Section 3.3.1.1 for details.

During the 52-week treatment period, individual patients may have their dose up-titrated if they experience suboptimal bleeding control on emicizumab. *Patients in Cohorts A, B, or C with ≥ 2 qualifying bleeds within a 12-week interval may have the opportunity to have their maintenance emicizumab dose increased to 3 mg/kg QW starting on Week 17, if they receive approval from the Medical Monitor. Of note, for patients from Cohorts B or C who have a dose up-titration, their dosing regimen will change from Q2W or Q4W to QW. Qualifying bleeds are defined as spontaneous and clinically significant, physician verified (e.g., with diagnostic imaging, clinical examination, photograph), and occurring while on prophylactic emicizumab at steady-state on the maintenance dose (after Week 5). Should patients meet protocol-defined criteria for up-titration, the investigator will contact the Medical Monitor to initiate a discussion about possible up-titration. Upon up-titration to the new maintenance dose of 3 mg/kg QW, the patient's schedule of assessments will reset to Week 1, and the next five visits must take place at the site.*

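### Counting bleeds from the first dose gives the common loading phase about twice the weight in Cohorts B and C as in Cohort A, which may shift the side-by-side regimen rates slightly (minor)

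*SAP*

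**What the plan says.** SAP 2.3.1 defines the efficacy period for all endpoints: "The start of the efficacy period for each individual patient is defined as the day of the first emicizumab dose". That is the first loading dose. Protocol 4.5.2 gives every cohort the same start: "Emicizumab treatment will begin with a loading dose of 3 mg/kg QW for the first 4 weeks". The regimens diverge only from Week 5.

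Follow-up differs by design. Protocol 3.1 opens Cohorts B and C only once, among other conditions, "2) Cohort A is fully enrolled". All cohorts nevertheless share one primary analysis. On its timing Protocol 3.2 says: "It will occur after all patients in the primary population of Cohort A have completed 52 weeks of treatment" (or have withdrawn). For the later cohorts it adds: "All data from patients enrolled in Cohorts B and C will be included regardless of follow-up time". Protocol 3.1 gives the expected length: "all available data from patients enrolled in Cohorts B and C (efficacy period approximately 6 months".

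SAP 4.4.1.1 estimates the bleed rate with a negative binomial model that has the efficacy period as offset, and also computes an ABR per patient. Protocol 6.4.1 assigns the model to Cohort A and the overall analysis, and the ABR to Cohorts B and C. SAP 4.1 groups outputs by original regimen (QW, Q2W, Q4W) with a total column. Neither document plans a rate restricted to maintenance or to a common follow-up window.

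**The concern.** An offset or an ABR makes unequal follow-up comparable only if the bleed rate is constant over the period. The protocol gives reason to doubt that here. Of the target median trough of 45 µg/mL, Protocol 3.3.1 says that it "is predicted to be achieved after treatment with 4 weekly doses of 3 mg/kg", and it reports fewer bleeds at higher concentrations. Protocol 3.1 also stops prophylactic bypassing agents the day before the first dose, while exposure is still building.

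If the loading rate is higher, the cohorts with shorter follow-up carry more of it per unit of time. The stated objective is efficacy at each regimen, and the regimens appear in adjacent columns. A reader could take a difference in loading share for a difference between regimens. Protocol Table 2 predicts a lower steady-state trough for Q4W (40.7 µg/mL) than for QW (51.5), so a real effect would point the same way, and the planned tables could not separate the two.

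**Working it through.** **Inputs.** Loading lasts 4 weeks (Protocol 4.5.2). Cohort A follow-up is 52 weeks, the minimum for completers of the primary population (Protocol 3.2). Cohorts B and C have 26 weeks, read from approximately 6 months (Protocol 3.1). Let k be the loading-phase bleed rate divided by the maintenance rate. The documents do not give k.

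**Loading share.** A: 4/52 = 7.7%. B and C: 4/26 = 15.4%. The ratio is 2.0.

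**Apparent rate ratio, B or C against A, with equal maintenance rates.** In units of the maintenance rate, the average is (4k + 48)/52 in A and (4k + 22)/26 in B or C.

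| k | B or C | A | Ratio |
|---|---|---|---|
| 0.5 | 24/26 = 0.923 | 50/52 = 0.962 | 0.96 |
| 1 | 1.000 | 1.000 | 1.00 |
| 1.4 | 27.6/26 = 1.062 | 53.6/52 = 1.031 | 1.03 |
| 1.7 | 28.8/26 = 1.108 | 54.8/52 = 1.054 | 1.05 |
| 2 | 30/26 = 1.154 | 56/52 = 1.077 | 1.07 |
| 3 | 34/26 = 1.308 | 60/52 = 1.154 | 1.13 |

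If Cohort A averaged 72 weeks (assumption), its average would be (4k + 68)/72, and the ratios at k = 2 and 3 would be 1.09 and 1.18.

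**What the protocol implies for k.**

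1. *Reproducing the predicted trough.* A one-compartment model fitted to Table 2 (absorption 0.464 and elimination 0.0214 per day, a half-life of ln 2/0.0214 = 32 days, within the 4-5 weeks in Protocol 1.2) gives troughs of about 14, 26, 37 and 46 µg/mL after loading doses 1 to 4. The last agrees with the plan's 45. Mean concentrations in Weeks 1 to 4 are about 10, 24, 35 and 45.
2. *Concentrations behind Table 1.* With linear kinetics and an average of 53.0 µg/mL at 1.5 mg/kg QW, weekly doses of 0.3, 1 and 3 mg/kg correspond to 53.0 × 0.3/1.5 = 10.6, 53.0 × 1/1.5 = 35.3 and 53.0 × 3/1.5 = 106 µg/mL.
3. *Residual bleeding.* The mean ABR reductions of 74.7%, 85.8% and 93.0% leave 25.3%, 14.2% and 7.0%.
4. *Linear interpolation.* Maintenance at 53 µg/mL: 14.2 − (53 − 35.3)/(106 − 35.3) × 7.2 = 12.4%. Weeks 1 to 4: 25.3, 19.4, 14.3 and 13.2%, mean 18.1%. So k = 18.1/12.4 = 1.46.
5. *Sensitivity.* If residual bleeding is 100% at zero concentration, averaging over the rising Week 1 curve gives 35.3% for that week. The four-week mean is 20.6%, and k = 20.6/12.4 = 1.66.

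The rough range is therefore k = 1.4-1.7, a shift of 3-5%.

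**Chance error.** Assume a maintenance ABR of 1, negative binomial dispersion 1, 10 patients and 26 weeks, with k = 1. The mean count per patient is 26/52.18 = 0.498, and its variance is 0.498 + 0.498² = 0.746. The SD of the cohort ABR is √(0.746/10)/0.498 = 0.55, which a simulation also gave. At k = 2 the systematic shift on this scale is about 1.15 − 1.08 = 0.07.

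**End of study.** With 52 weeks in B and C and an assumed 104 in A, the ratio is [(4k + 48)/52]/[(4k + 100)/104]: 1.04 at k = 2 and 1.07 at k = 3.

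**The case against.** The strongest reply is that nothing planned is biased. SAP 4 and 4.4 rule out formal testing. The bleed objectives are the on-treatment rate, the within-patient historical comparison (Cohort A only) and up-titration, and none compares regimens. Starting at the first dose is a legitimate definition of the overall on-treatment rate. Listings flag the dose for each event, so loading-phase bleeds can be found. Cohorts B and C are treated for at least 52 weeks and are analysed again at the end of the study. All of this stands and keeps the point minor. It does not remove the point, because the adjacent regimen columns remain and no maintenance-only rate is tabulated.

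A reader might infer that Q2W and Q4W could look 24% or 41% worse. Those figures need k = 5 or 10, and nothing in the documents supports such values. Table 1 places even k = 2 towards the high end, although it rests on only 6 patients per dose.

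A reader might also infer that the whole of Cohort A has a loading share of 8% or less. That holds only for those who complete 52 weeks. Early withdrawals have a larger share, and so do children under 2 years who enroll late and are included whatever their follow-up.

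**Conclusion.** The imbalance in loading share is structural and follows directly from the documents, taking approximately 6 months as 26 weeks. Its effect on the rates depends on k. The shift is about 3-5% against Q2W and Q4W at k = 1.4-1.7, 7% at k = 2, 13% at k = 3, zero at k = 1, and in the other direction below 1. The exposure build-up and exposure-response in the protocol favour k above 1 but do not establish it.

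The shift is systematic and the same for B and C, but several times smaller than chance error with about 10 patients per cohort. It would be wrong to conclude that the first-dose start is an error, or that a planned regimen comparison is invalid: the definition suits the overall rate, and no such comparison is planned. The point is minor. What is missing is a supplementary rate suited to reading across regimens.

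**What to change.** Keep the first-dose analysis as it is. Add to SAP 4.4.1.1 a supplementary bleed rate by original regimen that counts bleeds and person-time from Week 5 Day 1 only, with the end of the efficacy period and the separate handling of up-titrated time left as in SAP 2.3.1. State that any descriptive comparison of regimens will rest on this table. With equal, constant maintenance rates its expected ratio is 1.00 for every k.

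Truncating Cohort A at the median follow-up of Cohorts B and C is an optional extra. It equalises the loading shares only approximately, because follow-up within B and C varies around that median.

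The cost is one more table run on data already collected, and 4/26 = 15% less person-time in Cohorts B and C.
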